This approval is issued under Colorado State University's Federal Wide Assurance 00000647 with the Office for Human Research Protections (OHRP). If you have any questions regarding your obligations under CSU's Assurance, please do not hesitate to contact us.

Please direct any questions about the IRB's actions on this project to:

IRB Office - [contact]; [contact]
[name], Senior IRB Coordinator - [contact]; [contact]
[name], IRB Biomedical Coordinator - [contact]; [contact]

[name]

Continuing renewal has been reviewed at the convened meeting on March 22, 2018. Continuation has been approved to recruit the remaining participants with the approved recruitment and consent procedures. This renewal acknowledges an

Research Integrity & Compliance Review Office
Office of the Vice President for Research
[name] eprotocol
[contact]
[contact]

error in the initial approval letter generated by the IRB in that it should have stated approval for recruitment of 60 participants. This renewal includes two deviation reports that were assessed and two proposed amendments in response to the reports. These amendments include expanding enrollment to include participants with 10-day course of antibiotics with medical monitor support and increased enrollment a total of 200 participants. This number is to ensure participants completing the study will amount to 60 individuals. This is in response to large number of screen fails and withdrawals. Approved documents include: Consent, version dated 01March2018.

Approval Period: March 22, 2018 through March 21, 2019
Review Type: FULLBOARD
IRB Number: 00010468
Funding: AstraZeneca

Continuing review.....	1
Personnel Information.....	3
Subject Population.....	6
Study Location.....	7
General Checklist.....	7
Funding.....	9
Expedited Paragraphs.....	10
Purpose, Study Procedures, Background.....	12
Radioisotopes or Radiation Machines.....	19
Medical Equipment for Human Subjects and Laboratory Animals; Investigational Devices.....	20
Drugs, Reagents, or Chemicals.....	20
Subject Population (a-g).....	21
Subject Population (h-m).....	24
Risks.....	27
Benefits, Procedures to Maintain Confidentiality.....	32
Potential Conflict of Interest.....	33
Informed Consent.....	34
Assent Background.....	35
HIPAA.....	35
Attachments.....	37
Obligations.....	42

Event History.....	43
--------------------	----

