2. Weight loss associated with dietary counseling and the use of Dapagliflozin (SGLT2 inhibition) is characterized by normal circulating satiety signals rather than the usual diet-induced changes in circulating peptides that increase hunger and reduce satiety.

c) Proposed Start Date (may not precede IRB approval date):

On receipt of IRB approval.

2.

Study Procedures (If this is a student project, the methods section of the thesis or dissertation proposal must be attached in section #16 - Attachment section.)

a) In lay language, describe all the procedures, from screening through end-of-study, that the human subject must undergo in the research project, including study visits, drug treatments, randomization and the procedures that are part of standard of care. Please note: Do NOT respond "See Attachment Section." If you would like to add tables, charts, etc., attach those files in the Attachment section (#16).

OVERVIEW

This is a randomized, prospective, placebo-controlled, double blind, repeated measures study. 60 overweight/obese adults (body mass index > 27.5 kg/m²) will be recruited for participation and randomly assigned to one of two 12 week treatments: (1) daily oral administration of Dapagliflozin with dietary counseling to promote weight loss; or, (2) daily oral administration of a placebo with dietary counseling to promote weight loss.

Study participants will report to the research facilities on the Colorado State University main campus on 29 separate occasions:

Visit 1: study participants will undergo screening: medical history, 12-lead electrocardiogram and blood pressure assessment at rest and during incremental exercise to volitional exhaustion, blood sampling, and measurement of body composition.

Visit 2: an oral glucose tolerance test will be performed and resting metabolic rate and blood pressure will

Protocol Title: Does Dapagliflozin Provide Additional Health Benefits To Dietary Counseling For Weight Loss?
Clinical Research Protocol Title: Dapagliflozin Promotes Favorable Health Benefits That Are Independent Of Weight Loss In Overweight/Obese Adults

Protocol Type: Biomedical

Date Submitted: 03/01/2018

Approval Period: Draft

Important Note: This Print View may not reflect all comments and contingencies for approval. Please check the comments section of the online protocol.
Questions that appear to not have been answered may not have been required for this submission.
Please see the system application for more details.

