Blood sampling – Blood (~ 20 ml) will be sampled from an antecubital or hand vein for subsequent analysis of circulating factors pertinent to inclusion/exclusion criteria, including glucose, aspartate aminotransferase, alanine aminotransferase, and total bilirubin. These blood analyses will be performed in on-site (Piccolo Xpress, Abaxis, Union City, CA). Testing for Hepatitis B/C will be performed at a local, external clinical lab (e.g. University of Colorado-Health North). Per the Medical Monitor's discretion follow up blood draws maybe requested.

Visit 2: Resting Metabolic Rate (ventilated hood technique, indirect calorimetry) for 45 minutes and blood pressure will be measured. An oral glucose tolerance test will be performed.

Protocol Title:	Does Dapagliflozin Provide Additional Health Benefits To Dietary Counseling For Weight Loss? Clinical Research Protocol Title: Dapagliflozin Promotes Favorable Health Benefits That Are Independent Of Weight Loss In Overweight/Obese Adults
Protocol Type:	Biomedical
Date Submitted:	03/01/2018
Approval Period:	Draft
Important Note:	This Print View may not reflect all comments and contingencies for approval. Please check the comments section of the online protocol. Questions that appear to not have been answered may not have been required for this submission. Please see the system application for more details.

These procedures are standard for our lab. Each of the procedures is currently active in other IRB-approved protocols (e.g. 14-5201H).

Blood pressure will be determined three times using the left arm via standard procedures. Each assessment will be separated by 3 minutes. The mean of the three measurements will be recorded.

Participants will report to the laboratory early in the morning, following a 12-hour fast and 24-hour abstention from exercise. An intravenous catheter will be inserted into an antecubital or hand vein and kept patent with a saline drip. Following baseline blood sampling for fasting glucose and insulin, participants will ingest 75 g of dextrose dissolved in 250 ml of water over 10-minutes. Venous blood (~ 9 ml) will be sampled at time 0 (baseline) and 5, 10, 15, 20, 30, 45, 60, 75, 90 105 and 120 minutes for determination of concentration of blood glucose (2300 STAT Plus Glucose Lactate Analyzer, YSI Inc., Yellow Springs, Ohio), and insulin (commercially available assay).

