Baseline (pre-counselling) differences between placebo and SGLT2 inhibition groups were compared using independent Student t-Tests. Consistent with the experimental design (randomized, double-blind, parallel, repeated measures) the influence of SGLT2 inhibition on the physiological responses to dietary counselling was examined using two-way (group: placebo vs. SGLT2 inhibition x time: before vs. after dietary counselling) analysis of variance (ANOVA). The influence of SGLT2 inhibition and dietary counselling on the dynamic responses to oral glucose ingestion were examined using three-way ANOVA (placebo vs. SGLT2 inhibition x before vs. after dietary counselling x time points during the OGTT). Pairwise multiple comparison procedures were performed using the Holm-Sidak Method. Relations of interest were described using Pearson product-moment correlations. The level of statistical significance was set at $P<0.05$. Data are reported as mean and standard deviation, unless otherwise indicated. Calculations were performed using commercially available statistical software (SigmaStat 3.0, Systat Software Inc., San Jose, California, USA).

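### The three-way OGTT ANOVA states no sphericity correction: if none was applied, terms involving OGTT time would reject a true null in about 7–13% of trials, not 5%, under moderate to strong serial correlation

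*Combined protocol and SAP*

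**What the plan says.** The SAP is one paragraph at the end of the combined document. For most outcomes, "the influence of SGLT2 inhibition on the physiological responses to dietary counselling was examined using two-way" ANOVA with factors group and before/after. The OGTT responses "were examined using three-way ANOVA (placebo vs. SGLT2 inhibition x before vs. after dietary counselling x time points during the OGTT". That sentence names three crossed factors and nothing else: no participant factor, error strata, covariance model, test of sphericity or correction for its failure.

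The term repeated measures appears as a design label in the sentence on the two-way model: "Consistent with the experimental design (randomized, double-blind, parallel, repeated measures". The protocol overview (section 2a) uses it too: "This is a randomized, prospective, placebo-controlled, double blind, repeated measures study". The SAP names the package, "Calculations were performed using commercially available statistical software (SigmaStat 3.0", but not the procedure run in it. The only multiplicity provision is "Pairwise multiple comparison procedures were performed using the Holm-Sidak Method". It covers pairwise comparisons and does not change the interaction F tests.

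Under section 2a, Visit 2, venous blood "will be sampled at time 0 (baseline) and 5, 10, 15, 20, 30, 45, 60, 75, 90 105 and 120 minutes" for glucose and insulin. Visit 28 repeats the test. The IRB renewal letter gives the intended number of completers: "This number is to ensure participants completing the study will amount to 60 individuals".

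**The concern.** Samples from one person taken 5 to 15 minutes apart are serially correlated. Neighbouring samples then resemble each other more than distant ones, so differences between pairs of time points do not share a common variance. An uncorrected repeated-measures F test needs that common variance (sphericity) for any within-participant factor with more than two levels. OGTT time has 12 levels and visit has two, so the exposure lies in the terms containing OGTT time.

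The SAP's stated interest is in the dynamic response to oral glucose. An effect of the drug on the change in curve shape is tested by group x visit x OGTT time, which is an exposed term. An overall shift of the curve is tested by group x visit, which is not exposed. The SAP does not say which of the two is the treatment test. That is a separate gap: it leaves the claim open to two tests but does not itself inflate either one.

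**Working it through.** **Inputs from the documents.** Two arms; two visits; 12 OGTT times (0 to 120 min, unevenly spaced); 60 completers; significance at P<0.05. **Assumed, because not given:** 30 per arm, and all variances and correlations.

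**Degrees of freedom.** Three-way numerator: (2−1)(2−1)(12−1) = 11. Participants within arms: 60−2 = 58. Error: 58 × 11 = 638. Group x visit has 1 and 58.

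**Greenhouse-Geisser.** Let M be the covariance matrix of 11 orthonormal contrasts over OGTT time. Then ε = tr(M)² / [11·tr(M²)], which equals 1 under sphericity. The observed F is referred to 11ε and 638ε degrees of freedom.

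| ε | df | 5% critical F | Uncorrected P at that F |
|---|---|---|---|
| 1 | 11, 638 | 1.80 | 0.05 |
| 0.66 | 7.26, 421.08 | 2.01 | 0.025 |
| 0.30 | 3.30, 191.40 | 2.57 | 0.003 |

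An uncorrected P between 0.025 and 0.05 would therefore not survive correction at ε = 0.66. At ε = 0.30 the same holds for any P between 0.003 and 0.05.

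**Null simulation, repeated-measures reading.** 3,000 trials per setting, simulation standard error about 0.4 to 0.6 points. Relative variances: residual 1, between-person 1, person-by-visit 0.25. The first row checks that the nominal 5% is reproduced when sphericity holds.

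| Residual correlation | ε | Three-way, uncorrected | Three-way, corrected | Group x visit |
|---|---|---|---|---|
| None (spherical) | 1.00 | 5.1% | 3.9% | 4.9% |
| 0.3 between adjacent samples | 0.87 | 6.6% | 4.3% | 4.9% |
| 0.5 between adjacent samples | 0.67 | 8.4% | 4.6% | 4.8% |
| 0.7 between adjacent samples | 0.47 | 11.5% | 5.6% | 5.4% |
| 0.9 between adjacent samples | 0.29 | 12.7% | 4.6% | 4.7% |
| 0.5 per 15 min, actual times | 0.51 | 9.3% | 4.5% | 5.3% |
| 0.8 per 15 min, actual times | 0.29 | 12.9% | 4.8% | 4.7% |
| 0.9 per 15 min, actual times | 0.24 | 13.7% | 5.0% | 5.3% |

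Uncorrected group x OGTT time (5.6% to 14.2%) and visit x OGTT time (5.6% to 13.6%) behave in the same way.

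**Sensitivity to noise.** A second set of eight assumed variance structures, with independent noise at 2–15% of variance and 6,000 runs each, gave 7–13% uncorrected and 4–5% corrected for the three-way term. With independent noise raised to 40–70% of variance, the uncorrected rate fell to 5.4–7%. One setting with noise 0.5 and serial variance 0.2 (ε = 0.95) gave 5.0%.

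**Two candidate terms.** Two independent tests at 5% give 1 − 0.95² = 9.75% for at least one false positive. By simulation, at least one of group x visit and the three-way term is significant in 12–16% of null trials uncorrected and 8–10% corrected. Correction alone does not bring the pair to 5%.

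**Contrast: one residual, no participant strata.** Group rejects in about 36–63% of null trials and group x visit in about 14–39%. The interactions of group with OGTT time reject in about 0–4%.

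**The case against.** The SAP is a short, past-tense summary. It neither applies nor excludes a correction, and silence is not an error rate. Two sponsor protocol files are listed among the attachments but are not in the documents, and they may say more. This stands: the over-rejection is conditional on no correction having been applied.

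The size depends on assumed covariances, and its lower end is close to nominal. This also stands. Only the direction is firm, for serially correlated samples without dominant noise.

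The overall drug test, group x visit, is sound on the likely reading, so the problem is confined to curve-shape terms in one assessment among several. This stands too and limits the reach of the point.

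A reader might infer more than the documents support:

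- That observations were treated as independent. Nothing shows this, and both the protocol and the SAP call the design repeated measures. On that reading the three-way term would be conservative, while group and group x visit would over-reject.
- That all the omissions inflate the OGTT-time tests. Only the missing sphericity correction does so.
- That the investigators would report whichever term reached P<0.05. No such selection is described. The gap is only that the plan does not name one term.

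**Conclusion.** The point holds in a limited form. As written, and read as a repeated-measures ANOVA with no correction applied, the OGTT analysis does not hold 5% for terms involving OGTT time. The three-way test would reject a true null in about 7–13% of trials under moderate to strong serial correlation, and near 5% if independent noise dominates. Greenhouse-Geisser returns it to about 4–6%. Group x visit is unaffected.

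These rates rest on 60 completers split 30 per arm and on covariances that the documents do not supply. The unnamed treatment term is a separate, smaller gap, which matters only if either term may carry the claim. The plan should be corrected; the point does not show that any result is wrong.

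**What to change.** In the SAP:

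1. State that the OGTT model has participant and participant-by-visit error strata, and name the software procedure.
2. Apply Greenhouse-Geisser to every term involving OGTT time. Alternatively, fit a mixed model with a time-spaced or unstructured covariance. Unstructured over all 24 values needs 24 × 25 / 2 = 300 parameters from 60 people, so a time-spaced form is the more practical choice.
3. Say for each analyte whether group x visit or group x visit x OGTT time is the treatment test. If both may carry the claim, control the error across them, for example at 2.5% each.

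ANCOVA of post-treatment AUC on arm and baseline AUC is an optional summary test of the overall drug effect, not a required replacement. For an assumed 0.5 SD effect confined to 5–30 min, its simulated power is 11–24%, against 48–78% for the corrected interaction. For a uniform shift the AUC test has 63–99% and the interaction none.

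The cost is a few sentences, a reanalysis of data already collected and slightly less favourable P values for OGTT-time terms. Because the SAP is written in the past tense, a term named now should be reported as specified after the fact unless an earlier record shows otherwise.

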Please see the system application for more details.

Visits 4-27: During the first 6 weeks participants will meet with a study counselor 2 times per week for dietary counseling and measurement of body weight. During the second 6-week period they will meet 1-2 times per week for dietary counseling and body weight measurement, depending on whether or not they are meeting weight loss goals. If they are losing weight as prescribed, they will meet only once per week, but if they are not meeting weight loss goals they will meet 2 times per week. Participants will need to fast for 10 hours prior to the weigh-in. On 2 random counseling occasions between weeks 4 and 10, they will be asked to recall what they ate during the previous 24 hours. If participants fail to achieve their target body weight (within 1 kg or 2.2 lbs) on three consecutive weighing sessions, they will be provided with additional counseling and instructions to aid in achieving your target body weight.

During the first two weeks of the 12 week intervention, participants will ingest one pill daily (5 mg DAPA) and for the remaining 10 weeks participants will ingest 2 pills daily (a total of 10 mg DAPA). On 3 random weigh-in occasions between weeks 4 and 10, participants will be asked to recall what they ate during the previous 24 hours.

Visit 28: Resting Metabolic Rate Test, Oral Glucose Tolerance Test, and Blood Pressure will be measured (e.g. the final week of daily ingestion of Dapagliflozin). See description of Visit 2.

Visit 29: in the HPCRL appetite and hunger will be assessed this visit will occur in week 12 (e.g. during the final week of daily ingestion of Dapagliflozin). Body composition will be measured at this visit or early the following week (e.g. week 13). The study participants will also be given the 3-day food intake record form to be completed and returned to the research team.

b) Explain why human subjects must be used for this project.

Dapagliflozin is approved for human use. Due to potential species differences it would not be appropriate to perform these studies on experimental animals.

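### The SAP's three-way OGTT ANOVA has no rule for incomplete tests: one common fit drops a participant for a single missed draw, the other ignores within-participant correlation, and a mixed model avoids both.

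*Combined protocol and SAP*

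**What the plan says.** The OGTT is described under Visit 2 in item 2(a) of Purpose, Study Procedures, Background. After an oral glucose load, venous blood "will be sampled at time 0 (baseline) and 5, 10, 15, 20, 30, 45, 60, 75, 90 105 and 120 minutes", which is 12 time points, for glucose and insulin. All draws of one test come through a single line: "An intravenous catheter will be inserted into an antecubital or hand vein and kept patent with a saline drip". The test is repeated at the end of treatment: "Visit 28: Resting Metabolic Rate Test, Oral Glucose Tolerance Test, and Blood Pressure will be measured", with a reference back to the Visit 2 procedure.

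The Statistical Analysis Plan, at the end of the combined document, states that the OGTT responses are "examined using three-way ANOVA (placebo vs. SGLT2 inhibition x before vs. after dietary counselling x time points during the OGTT". Repeated measures are mentioned only in the preceding sentence, on the two-way ANOVA: "Consistent with the experimental design (randomized, double-blind, parallel, repeated measures". On software it says: "Calculations were performed using commercially available statistical software (SigmaStat 3.0". It names no repeated factors for the three-way model, no covariance structure, no analysis population, no imputation and no handling of missed samples. It also does not say that a participant with a missed draw is removed.

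The renewal letter gives the intended size. On the enrolment ceiling of 200 it says: "This number is to ensure participants completing the study will amount to 60 individuals".

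**The concern.** Each participant supplies a grid of 2 visits by 12 times. A participant can attend both tests and still have a gap, for example a missed time, a blocked catheter or a failed assay. The plan leaves open how such a person enters the model, and each of the two usual ways of fitting it has a fault.

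- **Classical repeated-measures ANOVA.** It needs complete participants. One empty cell discards the other 23 values.
- **Ordinary ANOVA on single samples.** Everyone stays in, but the 24 values from one person are treated as independent, so the tests use the wrong error term.

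The question here is isolated gaps in people who attended both tests, not whole missed visits. At stake is the precision of the drug comparison for OGTT glucose and insulin in a trial aiming at 60 completers, using blood that has already been drawn.

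**Working it through.** The documents state no power, effect size, SD, allocation ratio or missed-draw rate, so there is no planned figure to reproduce.

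**Inputs.** From the documents: 12 draws per OGTT, 2 OGTTs, 60 completers, a 5% significance level. Assumed: overall missed-draw rate p of 0.5%, 1% or 2%; 1:1 allocation; two-sided testing.

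**1. Grid size.** 12 x 2 = 24 values per participant per analyte; 60 x 24 = 1,440 in all.

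**2. Independent misses, complete-case fit.** Share dropped = 1 - (1 - p)^24.
- p = 0.5%: 1 - 0.995^24 = 11.3% (6.8 of 60)
- p = 1%: 1 - 0.99^24 = 21.4% (12.9 of 60)
- p = 2%: 1 - 0.98^24 = 38.4% (23.1 of 60)

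**3. Catheter run-out at the same overall rate.** Suppose the line fails at a random post-baseline draw and all later draws of that test are lost. A failure then loses between 1 and 11 draws, 6 on average. To give overall rate p, the failure probability per test is f = 12p/6 = 2p. Share dropped = 1 - (1 - 2p)^2.
- p = 0.5%: 1 - 0.99^2 = 2.0%
- p = 1%: 1 - 0.98^2 = 4.0%
- p = 2%: 1 - 0.96^2 = 7.8%

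**4. Intermediate clustering.** A beta-binomial model within each test, with intraclass correlation from 0.1 to 0.5, gives 7.6% to 3.1% dropped at p = 0.5%, 14.7% to 6.0% at 1%, and 27.4% to 11.8% at 2%.

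**5. Cost in precision.** Interval width ratio = 1/sqrt(share kept). For a two-arm contrast that has 80% power with all 60 (a chosen starting point), power = Phi(2.80 x sqrt(share kept) - 1.96), where 2.80 = 1.96 + 0.84.

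| p | Pattern | Kept | Interval wider by | Power |
|---|---|---|---|---|
| 0.5% | independent | 88.7% | 6% | 75% |
| 1% | independent | 78.6% | 13% | 70% |
| 2% | independent | 61.6% | 27% | 59% |
| 0.5% | run-out | 98.0% | 1% | 79% |
| 1% | run-out | 96.0% | 2% | 78% |
| 2% | run-out | 92.2% | 4% | 77% |

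This is a simple two-group contrast, used as a guide to scale. It is not the power of the three-way interaction test.

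**6. Behaviour of the methods.** In one simulated data set of 60 people, 13 of 1,440 samples (0.9%) were missing independently. A standard repeated-measures ANOVA routine, given the two within-person factors, refused the data as unbalanced. Restriction to complete participants kept 51 of 60 people and 51 x 24 = 1,224 samples, so 1,427 - 1,224 = 203 valid values were discarded. A mixed model with arm x visit x time terms used all 60 people and all 1,427 samples.

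**7. The ordinary-ANOVA reading.** Let P, V and E be the participant, participant-by-visit and residual variances. The change in one person's 12-sample mean has variance 2(V + E/12). Ordinary ANOVA uses 2(P + V + E)/12. The second is too small whenever P < 11V, so the arm x visit standard error would then be understated, and overstated otherwise. The documents give none of these variances, so the direction is open, but the error term is wrong except by coincidence.

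**The case against.** The strongest reply is that the deletion is inferred. The SAP nowhere says that incomplete participants are removed, the three-way sentence does not itself say repeated measures, and a general-linear-model or mixed fit could keep partial OGTTs. That stands: loss of participants belongs to one way of fitting the model and is not a stated rule. It does not clear the plan, because no method that handles gaps properly is specified.

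A reader might go further and infer that a third or more of the sample would be lost. The documents do not support that. No missed-draw rate appears anywhere, and the 38% figure needs both a 2% rate and independent misses. One catheter serves each test, so clustering is plausible, and run-out at the same 2% rate drops about 8%.

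Two other inferences also go too far. Deletion need not bias the result: if draws are missed at random the cost is precision only, and nothing in the documents links missed draws to adiposity. Nor does having its own model make the OGTT the primary outcome, since no primary endpoint is named.

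**Conclusion.** The point holds as a cheap improvement. The SAP's three-way ANOVA, with no rule for incomplete OGTTs, is inferior to a mixed model on either reading: one can drop participants who attended both tests, and the other ignores the correlation within them.

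The size is illustrative. For 0.5-2% of draws missing, complete-case fitting drops about 11-38% of participants under independence and about 2-8% under catheter run-out, with moderate clustering in between. The missing rates, the 1:1 allocation and the 80% starting power are assumptions. None of these figures is an expected loss for this trial.

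**What to change.** Replace the three-way ANOVA sentence with wording to this effect: OGTT glucose and insulin are each analysed with a linear mixed model fitted by REML to every available sample, with fixed effects for arm, visit, OGTT time and all their interactions, and a within-participant covariance structure that allows for participant and for visit within participant. The drug effect is read from the arm x visit and arm x visit x time terms. Report, by arm and visit, how many OGTTs were incomplete and how many participants entered the model.

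The cost is SAP wording and a mixed-model routine, with no new data or participants. The model assumes that missing samples are missing at random, and the covariance structure must be stated. The SAP is written in the past tense, so if the change is made after the data were seen, the analysis must be labelled post hoc.

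A per-visit time-weighted mean with interpolation is not an equivalent substitute. It cannot fill a missing 0- or 120-minute draw (2 end points x 2 visits = 4 of the 24 cells) or a run-out, so participants could still be lost.
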